
2.5.2 Chronic GVHD

Patients developing sign/symptoms of chronic GVHD (CGVHD) will have symptoms recorded on the CGVHD scoring form at the scheduled follow-up visits.

2.5.3 Studies of GVHD Biology

Laboratory studies to investigate biologic parameters of response and differential response to the four study drugs will be included in this clinical trial.

- Skin biopsies (pre and on Day 28 of study therapy) for clinical diagnostic pathology, immunopathology, and other investigations (Appendix C-4) are to be performed.
- Immunophenotyping: Cytokine assays to correlate with GVHD response and cytokine gene polymorphisms will be examined (Appendix C-1).
- Proteomics (Appendix C-6) of sera collected before and after therapy will be performed.

Definite and Possible Manifestations of Chronic GVHD

Organ System	Definite manifestations of chronic GVHD	Possible manifestations of chronic GVHD
Skin	Scleroderma (superficial or fasciitis), lichen planus, vitiligo, scarring alopecia, hyperkeratosis pilaris, contractures from skin immobility, nail bed dysplasia	Eczematoid rash, dry skin, maculopapular rash, hyperpigmentation, hair loss
Mucous membranes	Lichen planus, non-infectious ulcers, corneal erosions/non-infectious conjunctivitis	Xerostomia, keratoconjunctivitis sicca
GI tract	Esophageal strictures, steatorrhea	Anorexia, malabsorption, weight loss, diarrhea, abdominal pain
Liver	None	Elevation of alkaline phosphatase, transaminitis, cholangitis, hyperbilirubinemia
GU	Vaginal stricture, lichen planus	Non-infectious vaginitis, vaginal atrophy
Musculoskeletal/ Serosa	Non-septic arthritis, myositis, myasthenia, polyserositis, contractures from joint immobilization	Arthralgia
Hematologic	None	Thrombocytopenia, eosinophilia, autoimmune cytopenias
Lung	Bronchiolitis obliterans	Bronchiolitis obliterans with organizing pneumonia, interstitial pneumonitis

From BMT CTN MOP Chapter 2

CHAPTER 3

3 STUDY ENDPOINTS

3.1 Primary Endpoint

The primary endpoint is proportion of CR at Day 28 of therapy. **CR is defined as resolution of all signs and symptoms of GVHD in all evaluable organs in comparison to Day 1 scoring.** For a response to be scored as CR at Day 28 or later, the participant must still be in CR on that day and have had no intervening salvage therapy for an earlier progression, PR or NR.

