2.4.8 GVHD Progression or Non-response

If acute GVHD **progresses** (new organ involvement or increased organ specific symptoms sufficient to increase the organ stage by one or more) within 7 days or there is **no response** (no reduction in any GVHD organ staging) within 14 days, the patient may be treated with alternative secondary GVHD therapy and/or taken off assigned study therapy. Patient must still be followed for all study endpoints.

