3.2 Secondary Endpoints

3.2.1 Proportion of Partial Response (PR), Mixed Response (MR), No Response (NR) and Progression

Partial response (PR) is defined as improvement in one or more organs involved with GVHD symptoms without progression in others. For a response to be scored as PR at Day 28 or later, the participant must still be in PR on that day and have had no intervening salvage therapy for an earlier progression, PR or no response (NR). **Mixed response (MR) is defined as improvement in one or more organs with deterioration in another organ manifesting symptoms of GVHD or development of symptoms of GVHD in a new organ.** **Progression is defined as deterioration in at least one organ without any improvement in others.** **No response (NR) is defined as absence of any improvement or progression as defined.** Scoring of PR, MR, NR and progression are in comparison to the participant's GVHD status (score) on Day 0 of the study.

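### The rescue clause in the Day 28 CR definition omits mixed response, so as written a mixed responder cleared by second-line therapy can be counted as a CR for the study agent

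*Combined protocol and SAP*

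**What the plan says.** Section 3.1 sets the primary endpoint. A patient scored as CR on Day 28 must be in CR that day and "have had no intervening salvage therapy for an earlier progression, PR or NR". The PR sentence in 3.2.1 repeats the same three reasons.

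Section 3.2.1 then separates the response categories:

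- Mixed response: "Mixed response (MR) is defined as improvement in one or more organs with deterioration in another organ manifesting symptoms of GVHD", or GVHD symptoms in a new organ.
- Progression: "Progression is defined as deterioration in at least one organ without any improvement in others".
- PR: "Partial response (PR) is defined as improvement in one or more organs involved with GVHD symptoms without progression in others".
- NR: "No response (NR) is defined as absence of any improvement or progression as defined".

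Section 2.4.8, in the treatment plan, gives progression another meaning: "new organ involvement or increased organ specific symptoms sufficient to increase the organ stage by one or more", with no condition on the other organs. If this occurs within 7 days, or if no organ stage falls within 14 days, "the patient may be treated with alternative secondary GVHD therapy and/or taken off assigned study therapy". Follow-up for every endpoint continues.

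Section 3.2.2 handles added therapy differently. Any additional GVHD therapy by Day 14 is a primary treatment failure, whatever prompted it.

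**The concern.** The rescue clause exists so that a remission obtained with another GVHD agent is not credited to the study agent. It works by listing reasons for salvage, and the list leaves out one of the plan's own response categories. A mixed responder is a likely candidate for rescue, because one organ is getting worse.

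The primary endpoint carries the decision. Section 5.5 compares each arm with a fixed 35% and makes no comparison between arms, so misattributed CRs in one arm are not offset by the same error in a control. The margin is also narrow: Table 5.6 puts the cutoff at 21 of 45, and a single reclassified patient separates 20 (fail) from 21 (pass). If the clause can be read two ways, centers could score the same record differently.

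**Working it through.** **1. Does mixed response fall under any listed reason, using the 3.2.1 definitions?**

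| Listed reason | Requirement in 3.2.1 | Mixed responder |
|---|---|---|
| Progression | no organ improves | at least one organ improves: not met |
| PR | no other organ worsens | another organ worsens or is newly involved: not met |
| NR | no improvement at all | at least one organ improves: not met |

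On these definitions the clause does not reach a mixed responder.

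**2. A test record.** Day 1: skin stage 3, gut stage 0. Day 6: skin 1, gut 2. A second-line agent starts on Day 6. Day 28: every organ at stage 0.

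- Under 3.2.1 the Day 6 status is mixed response, because skin improved and gut is new. Salvage was not for a listed reason, so the Day 28 CR stands.
- Under 2.4.8 the Day 6 status is progression (new organ, within 7 days), so alternative therapy is allowed. If that meaning also governs 3.1, salvage was for progression and the CR is void.
- Under 3.2.2 the same patient is a Day 14 treatment failure on either reading.
- If skin had stayed at 3 on Day 6, both meanings give progression and the CR is void. On the narrow reading, then, the fate of an identical rescue turns on a different organ.

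**3. Reproduce the plan's figures.** Inputs: Beta(3.5, 6.5) prior, 35% reference rate and success if the posterior probability exceeds 90% (5.5); futility at 4 or fewer CRs in 20 (5.6, 5.8); cutoffs in Table 5.6.

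Posterior probability of efficacy with x CRs in n = P(Beta(3.5 + x, 6.5 + n − x) > 0.35):

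| n | at cutoff | one CR fewer |
|---|---|---|
| 45 | 21: 0.925 | 20: 0.878 |
| 52 | 24: 0.934 | 23: 0.893 |
| 65 | 29: 0.930 | 28: 0.892 |

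All three cutoffs are confirmed.

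Probability that an arm passes, with true scored CR rate p, final size n and cutoff c:

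Pass(p) = Σ over x = 5 to 20 of P[Bin(20, p) = x] × P[Bin(n − 20, p) ≥ c − x]

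The mortality rule is left out. At p = 0.35 this gives 7.1% for n=45, 6.3% for n=52 and 6.9% for n=65, against 7% in Table 5.7. The plan's figure is reproduced.

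**4. Illustrate the sensitivity.** Let d be the percentage points of CR added by rescued mixed responders who would otherwise not be CRs. The documents give no value for d, so 1 to 3 points is an assumption. At n=45 it corresponds to 45 × 0.01 = 0.45 up to 45 × 0.03 = 1.35 patients per arm.

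| d | p | n=45, cutoff 21 | n=65, cutoff 29 |
|---|---|---|---|
| 0 | 0.35 | 7.1% | 6.9% |
| 1 | 0.36 | 9.2% | 9.5% |
| 2 | 0.37 | 11.8% | 12.6% |
| 3 | 0.38 | 14.8% | 16.5% |

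The calculation assumes that the historical 35% did not itself include rescued mixed responders.

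**The case against.** The strongest reply is that the test patient is already excluded. Section 2.4.8 allows the rescue because GVHD has progressed in its sense, so therapy given on that ground is naturally salvage for progression. Chapter 3 itself sometimes uses the word broadly: the PR definition speaks of progression in other organs, which cannot carry the patient-level meaning, and 3.2.3 treats any increase in symptoms or therapy after a response as progression. Section 2.5 also omits mixed response when listing who receives alternative therapy.

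This has force. A reader might infer that every rescued mixed responder will count as a CR, and the documents do not support that. Nor do they support the opposite: 2.4.8 is a treatment rule, nothing makes it govern scoring, and the endpoint chapter supplies its own narrower definition. What remains is an ambiguity in the primary endpoint.

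A second tempting inference is that the bias is large, because the background reports mixed response in 3 of 20 pentostatin patients (1.2.6) and 2 of 10 ONTAK patients (1.2.7). These are small earlier series, in steroid-resistant disease for pentostatin, whereas this trial enrols newly treated patients. They do not say how many mixed responders were rescued before Day 28 or cleared afterwards. Someone who turns mixed after Day 7 with a reduced organ stage meets neither trigger in 2.4.8, so rescue of all of them cannot be assumed. Some would have cleared without rescue and are not extra CRs. Finally, the plan does not say how the historical 35% treated rescue; if it was scored the same way, the bias shrinks or vanishes.

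**Conclusion.** The point holds as a gap and an ambiguity in the primary endpoint definition. On the endpoint chapter's own terms, a mixed responder cleared by second-line therapy can be counted as a Day 28 CR. On the treatment chapter's meaning of progression, the same patient can be excluded. No passage settles which applies, and 3.2.2 already counts the same added therapy by Day 14 as failure. The PR definition shares the gap.

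The size is unknown. The pass probabilities of 9.2% to 14.8% at n=45 show only how sensitive the rule is to a few misattributed CRs; they rest on an assumed addition of 1 to 3 points and on a historical rate free of such cases. A reader might also infer that the stated design figures are wrong. They are not: the cutoffs and the 7% error rate reproduce, and no sample size or power figure changes. The correction is worth making because it concerns the primary endpoint and costs little.

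**What to change.** In 3.1, and in the matching PR sentence of 3.2.1, replace the list of reasons with a rule based on the therapy itself. Suggested text: *A patient who receives any additional systemic agent for acute GVHD before the Day 28 assessment, whatever the response category at the time (progression, mixed response, PR or NR), is scored as not CR (or not PR).*

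Separately, reconcile the meanings of progression in 2.4.8 and 3.2.1 for scoring, by stating in chapter 3 which one its response categories and any remaining reference to progression use. Neither change affects when rescue is allowed or what is given.

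The cost is two sentences and one clarification. The weekly record in 2.5.1 already captures GVHD treatment, including a field for other agents, and 2.5 continues weekly scoring through week 8 for patients on alternative therapy, so no new data are needed. The downside is that the observed CR rate may be slightly lower.

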3.1.1 Staging and Grading of Acute GVHD

Staging*

	Stage 0	Stage 1	Stage 2	Stage 3	Stage 4
Skin	No rash	Rash < 25% BSA	25-50%	> 50% Generalized erythroderma	Plus bullae and desquamation
Gut	< 500 mL diarrhea/day	501-1000 mL/day	1001–1500 mL/day	> 1500 mL/day	Severe abdominal pain & ileus
UGI		Severe nausea/vomiting			
Liver	Bilirubin \leq 2 mg/dl	2.1-3 mg/dl	3.1-6mg/dl	6.1-15mg/dl	> 15 mg/dl

Grading Index of Acute GVHD*

	Grade A	Grade B	Grade C	Grade D
Skin	1	2	3	4
Gut	0	1-2	3	4
Upper GI	0	1		
Liver	0	1-2	3	4

*[See Appendix A, Endnote 28]

3.2 Secondary Endpoints

3.2.1 Proportion of Partial Response (PR), Mixed Response (MR), No Response (NR) and Progression

Partial response (PR) is defined as improvement in one or more organs involved with GVHD symptoms without progression in others. For a response to be scored as PR at Day 28 or later, the participant must still be in PR on that day and have had no intervening salvage therapy for an earlier progression, PR or no response (NR). **Mixed response (MR) is defined as improvement in one or more organs with deterioration in another organ manifesting symptoms of GVHD or development of symptoms of GVHD in a new organ.** **Progression is defined as deterioration in at least one organ without any improvement in others.** **No response (NR) is defined as absence of any improvement or progression as defined.** Scoring of PR, MR, NR and progression are in comparison to the participant's GVHD status (score) on Day 0 of the study.

3.2.2 Proportion of Primary Treatment Failures

No response, progression, administration of additional therapy for GVHD, or mortality by Day 14 post-initiation of treatment will be considered a primary treatment failure.

3.2.3 GVHD Flares

Flares are defined as any increase in symptoms of or therapy for acute GVHD after an initial response (i.e., progression from an earlier CR or PR). The rate of flares prior to Day 90 will be examined.

3.2.4 Immunosuppression Discontinuation

Immunosuppression discontinuation will be assessed by Day 90, Day 180 and Day 270. It is defined as the discontinuation of corticosteroids and all additional immunosuppressives, except cyclosporine or tacrolimus, for treatment of acute GVHD without subsequent flare by Day 90 post-initiation of therapy and later by discontinuation of all immunosuppressive medications, including cyclosporine or tacrolimus. Note that discontinuation of MMF will be 4 weeks later than other study drugs even in patients with CR.

3.2.5 Chronic GVHD

Chronic GVHD is defined per the BMT CTN Manual of Procedures (MOP) Chapter 2. The incidence of chronic GVHD at 9 months will be computed for each treatment arm.

3.2.6 Survival

Overall survival at Days 180 and 270 will be computed for each treatment arm.

3.2.7 Systemic Infections

All microbiologically documented infections occurring within three months of initiation of therapy will be reported by site of disease, date of onset, and severity. For definitions see the BMT CTN MOP. Post-transplant lymphoproliferative disorder will be reported through 9 months post-initiation of therapy.

CHAPTER 4

4 PATIENT ENROLLMENT AND EVALUATION

4.1 Enrollment and Randomization

Patients will be registered using the BMT CTN Advantage Electronic Data Capture (EDC). The following procedures shall be followed:

1. An authorized user at the clinical center completes the initial screening by entering patient demographics and Segment A information (inclusion/exclusion criteria) of the Eligibility Form within 48 hours of diagnosis of acute GVHD.
2. If the patient is eligible, a study number and random treatment assignment is generated.
3. A visit schedule based on treatment start date is displayed for printing.

If a connection is interrupted during a randomization session, the process is completely canceled and logged. A backup manual registration and randomization system will also be available to provide for short-term system failure or unavailability.

4.1.1 Randomization

Patients will be randomized within 48 hours of diagnosis of acute GVHD. Patients who have received MMF for GVHD prophylaxis, within 7 days of GVHD onset, will be randomized in a 1:1:1 ratio to receive ONTAK, pentostatin or etanercept. Patients who have not received MMF for GVHD prophylaxis will be randomized in a 2:1:1:1 ratio (MMF and the other three arms respectively) to one of the four treatment arms. Treatment should be initiated as soon as possible after randomization. A maximum of 48 hours is allowable.

No stratification factors will be used. Strata that were considered included: Grade B versus Grades C/D, age, unrelated donor, single organ versus multi-organ GVHD, full versus non-ablative conditioning, GVHD prophylaxis with a calcineurin inhibitor. However, none of these consistently identify GVHD patient cohorts with different CR rates. Therefore, it was decided that no stratification factors would be used in this trial.

4.2 Study Monitoring

4.2.1 Follow-up Schedule

The Follow-up Schedule for scheduled study visits is outlined in Table 4.2.1. A detailed description of each of the forms and the procedures required for forms completion and submission can be found in the Data Management Handbook and User's Guide.

Follow-up Assessments: The timing of follow-up visits is based on the date of randomization. Following randomization, the Transplant Center can print a Patient Visit Schedule listing target

dates for assessments. Weeks 1-8 visits are primarily for acute GVHD scoring. The subsequent visits are for follow-up reports.

Criteria for Forms Submission: Criteria for timeliness of submission for all study forms are detailed in the Data Management Handbook and User's Guide. Forms that are not received at the DCC within the specified time will be considered delinquent. Transplant Centers can view past due forms via the Web-based data entry system. A missing form will continue to appear until the form is entered into the DCC's master database, or until an exception is granted and entered into the Missing Form Exception File, as detailed in the Data Management Handbook and User's Guide.

Reporting Patient Deaths: The Recipient Death Information must be entered into the web-based data entry system within 24 hours of knowledge of a patient's death. If the cause of death is unknown at that time, it need not be recorded at that time. However, once the cause of death is determined, the form must be updated.

CIBMTR Data Reporting: All transplant centers participating in BMT CTN protocols are required to register all of their transplant patients, not just those enrolled on BMT CTN protocols, with the CIBMTR, using standard CIBMTR Preregistration and Transplant Essential Data Forms (instructions available at www.ibmtr.org). CIBMTR Day 100 Report Forms (including the Core, Graft and Disease Inserts) and CIBMTR Follow-up Forms (including the Core and Disease Inserts) are required for patients enrolled on BMT CTN protocols and will be submitted directly to the CIBMTR at the times specified in the Data Management Handbook and User's Guide.

Table 4.2.1
FOLLOW-UP SCHEDULE

Assessment Time	Target Day¹ (Days Post-Enrollment)
1 week	7 days
2 weeks	14 days
3 weeks	21 days
4 weeks	28 days
5 weeks	35 days
6 weeks	42 days
7 weeks	49 days
8 weeks	56 days
90 days	90 days
120 days	120 days
6 months	180 days
9 months	270 days

¹Target day range = ± 2 days up to Week 8, and ± 14 days for Days 90, 120, and ± 28 days for 6 and 9 months, post-randomization.

4.2.2 Assessments

All assessments are considered standard-of-care unless identified below by “*.”

Pre-Randomization

1. Recommended biopsy of involved tissue*
2. History and physical exam including height and weight
3. Pregnancy test (if applicable)
4. Complete acute GVHD staging and grading information including assessments of rash, diarrhea, nausea/vomiting, weight and liver function tests
5. CBC with differential, platelet count
6. Liver function tests (bilirubin, alkaline phosphatase, AST, ALT) plus creatinine
7. Tacrolimus/cyclosporine level
8. Samples for laboratory studies (see Appendix C)*

Post-Randomization

1. Recommended skin biopsy if skin involved on Day 28 (see Appendix C-4)*

2. Karnofsky or Lansky performance status on Days 28, 90, 180 and 270
3. Complete acute GVHD staging and grading information including assessments of rash, diarrhea, nausea/vomiting, weight and liver function tests weekly until Day 56, and 3, 4, 6 and 9 months, creatinine weekly until Day 28, and recommended creatinine on Days 35, 42, 49, 56, and 3, 4, 6, and 9 months.
4. Chronic GVHD evaluation (if present) 3, 4, 6 and 9 months
5. CBC with differential, platelet count weekly until Day 56
6. Toxicity evaluation weekly until Day 56
7. Steroid dose weekly until Day 56, and 3, 4, 6 and 9 months
8. Tacrolimus/cyclosporine levels weekly until Day 28
9. MMF levels in weeks 1 and 2 (4 levels at time 0, 1, 2, 6 hours on oral MMF; 0, 2, 4, 6 hours if on IV MMF) (see Appendix C-5)*
10. Samples for laboratory studies on Days 0, 14, 28 and 90 (see Appendix C)*
11. Infections through Day 90 and occurrence of Post-transplant Lymphoproliferative Disorder (PTLD) through Day 270.

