Treatment Description: The treatment schedules are as follows: **Etanercept** [25 mg subcutaneously twice weekly for up to 4 weeks; discontinue if in CR by 4 weeks]. Mycophenolate mofetil (**MMF**) [20 mg/kg (maximum 1 gm) PO or IV BID; continue through prednisone taper, then taper MMF over 4 weeks]. Denileukin Diftitox (**ONTAK®**) [9 mcg/kg IV Days 1, 3, 5, 15, 17, 19]. **Pentostatin** [1.5 mg/m² daily for 3 days; Days 1-3 and repeat Days 15-17].

All patients will receive methylprednisolone 2 mg/kg/day IV (or prednisone 2.5 mg/kg/day PO) divided in 2-3 daily doses for at least 7 days. Prednisone may be tapered as tolerated to no less than 0.75 mg/kg/day (methylprednisolone 0.6 mg/kg/day) at Day 28 of therapy. If not in CR at Day 28, patients will be followed for study endpoints, but assigned therapy can be continued or changed per institutional guidelines.

In addition to prescribed study drug plus corticosteroids, all patients should receive transfusion support per institutional practice; anti-infective prophylaxis directed towards CMV, gram positive (encapsulated) bacteria, pneumocystis carinii and fungal infections

[figure not shown]
Weekly GVHD organ stage scores, overall clinical grade, biopsy information for GVHD and relevant differential diagnosis will be recorded and reported to the BMT CTN Data Coordinating Center (DCC).

Accrual Objective: A maximum of 180 patients, but at most 65 per arm, will be randomized to one of the four treatment arms. After 80 patients are evaluable for the primary endpoint, if in any experimental arm, observed responses suggest a posterior probability > 85% that an arm will have a true CR < 35%, enrollment to the arm will cease and the arm will be excluded from further consideration due to lack of evidence for efficacy.

Accrual Period: The estimated accrual period is 12 months.

Study Duration: Patients will be followed for 9 months following initiation of therapy.

STUDY DESIGN SCHEMATIC

* Steroids = 2.5 mg/kg prednisone/day PO or IV equivalent in methylprednisolone (2 mg/kg) divided 2-3 times daily

Primary Endpoint:
Proportion of CR at Day 28 of therapy.

STUDY SCHEMA

Aim: To determine if any of four new agents, given in addition to corticosteroids as initial therapy for acute GVHD improves response rate and overall clinical outcome.

Inclusion Criteria	Exclusion Criteria

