2.4.3.2 MMF drug supply

MMF will be provided by the BMT CTN for up to 8 weeks. Oral MMF is available as 500 mg tablets and 250 mg hard gelatin capsules in bottles of 100 each. Capsules should be stored at room temperature. A liquid suspension is also available (200 mg/mL, 225 mL bottle) and should be stored at 25°C. Once reconstituted the solution may be stored at room temperature or under refrigeration (do not freeze) for 60 days. Enteric coated MMF (Myfortic) should not be used.

Intravenous: MMF for intravenous use will be supplied as a lyophilized powder. It will be reconstituted by injecting 5% Dextrose in Water (D5W) into each vial.

Intravenous MMF does not contain an antibacterial preservative; therefore, it should be prepared under aseptic conditions. Reconstitute each vial with 14 mL D5W. Gently shake vial to dissolve the drug. Further dilute into D5W for a final concentration of 6 mg/mL. Dilute 1-g doses in 140 mL D5W and 1.5-g doses into 210 mL D5W. Intravenous mycophenolate is incompatible

with normal saline and other saline containing diluents. Only D5W solution should be used for reconstitution and infusion solution. Infusion lines should be flushed with D5W only.

The Pharmacist at each center should prepare each dose of drug to avoid errors. Because of the potential teratogenic effects of MMF, pharmacists should follow the guidelines established at their centers for the preparation of similar types of solutions.

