2.4.3.7 Discontinuation

If in CR at Day 28, continue MMF at the same dose through the completion of the prednisone taper, then taper MMF and discontinue over four more weeks.

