2.4.9 GVHD Complete Response or Partial Response

Complete response at Day 28 is the primary endpoint evaluation for the trial. Patients with complete response will continue corticosteroids according to the taper above. Etanercept, ONTAK, or pentostatin will not be further administered. MMF (as per Section 2.4.3 above) will be continued through the duration of prednisone taper and then tapered over 4 weeks and stopped.

Patients not in CR at Day 28 will not have further study drug supplied (with the exception of MMF), but may continue assigned study drug or alternative therapy at the investigator or institutional discretion. Patients must still be followed for all study endpoints.

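### Scheduled CBC and toxicity evaluation stop at Day 56, but MMF in a Day 28 complete responder nominally runs to about Day 98, so late non-serious toxicity on that arm goes largely unrecorded

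*Combined protocol and SAP*

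**What the plan says.** Post-randomization items 5 and 6 of Section 4.2.2 read "CBC with differential, platelet count weekly until Day 56" and "Toxicity evaluation weekly until Day 56". In Table 4.2.2 neither row is marked at Day 90, 120, 180 or 270. The section opens with "All assessments are considered standard-of-care unless identified below by" an asterisk. Neither item has one, so both count as usual care.

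Three places set the length of MMF treatment:

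- Synopsis, Treatment Description: "continue through prednisone taper, then taper MMF over 4 weeks".
- Section 2.4.3.7, on complete responders: "continue MMF at the same dose through the completion of the prednisone taper, then taper MMF and discontinue over four more weeks".
- Section 2.4.9: MMF "will be continued through the duration of prednisone taper and then tapered over 4 weeks and stopped".

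Both suggested steroid tapers in Section 2.4.6.1 end on Day 70. Section 2.4.6 sets a minimum steroid dose for responders through Day 28 and leaves later dosing to the treating physician.

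Two statements point to an earlier end for MMF. Section 2.4.3.2 says "MMF will be provided by the BMT CTN for up to 8 weeks", and a note in Section 3.2.4 has MMF trailing the other agents by four weeks.

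**The concern.** The other three agents finish planned dosing well inside the weekly recording window: pentostatin on Day 17, ONTAK on Day 19 and etanercept at about Day 28. Only MMF is planned to continue past it, and only in complete responders, the patients who define an agent's success.

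Section 2.4.3.4 lists leukopenia, diarrhea and vomiting among MMF's risks. Section 2.4.3.5 halves the dose below an ANC of 1000/μL and stops it below 500/μL, with no time limit, yet no study CBC is scheduled after Day 56 to show how often this happens. Expected, non-serious leukopenia also falls outside both the expedited reports and the DSMB summary in Section 4.2.4.

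Section 5.10 names toxicities among the considerations that could weigh heavily in judging each agent for Phase III. If MMF's late toxicity goes unrecorded while the others' planned exposure is fully observed, MMF may look somewhat safer than it is.

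**Working it through.** The plan states no end day for MMF and no length for the gap, so there is no figure to reproduce. The check is a day count.

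**Inputs.** Last scheduled CBC and toxicity evaluation: Day 56 (4.2.2, Table 4.2.2). Steroids stop: Day 70, suggested (2.4.6.1). MMF taper: 28 days (2.4.3.7, 2.4.9). Planned MMF arm size: 45, cap 65 (5.3, 5.1).

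**Nominal gap.**

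- MMF ends on Day 70 + 28 = Day 98.
- Uncovered: 98 − 56 = 42 days; 42/98 = 43%.
- Split: 70 − 56 = 14 days at full dose, then 28 on taper.
- Full-dose days covered: 56/70 = 80%; uncovered: 14/70 = 20%.
- Dose-weighted, assuming a linear taper: total 70 + 28/2 = 84 full-dose-equivalent days; uncovered 14 + 14 = 28; 28/84 = 33%.
- With a treatment start 0–2 days after randomization and the ±2-day Week 8 window, the gap is 40 to 46 days.

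**Sensitivity to the steroid stop day S.** Gap = (S + 28) − 56 = S − 28. Values of S other than 70 are assumptions.

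| S | MMF ends | Uncovered days | Share |
|---|---|---|---|
| 30 | 58 | 2 | 3% |
| 42 | 70 | 14 | 20% |
| 56 | 84 | 28 | 33% |
| 70 | 98 | 42 | 43% |
| 90 | 118 | 62 | 53% |

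Under the dosing sections the gap is never zero: Section 2.4.6 keeps responders on steroids through Day 28, so S exceeds 28. At S = 30 it is no larger than the visit window.

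**The Day 56 reading.** Eight weeks of supply is 8 × 7 = 56 days, and four weeks after a four-week drug is 28 + 28 = Day 56. Either would make the gap zero. But an end at Day 56 after a 28-day taper requires that taper to start by Day 28, when responders must still be on steroids. All three dosing statements start the MMF taper only after the steroid taper, and Section 2.4.3.2 limits supply, not dosing.

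**Patients affected** (assumed CR rate 35–50%).

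- 45 on MMF: 45 × 0.35 = 15.75 to 45 × 0.50 = 22.5, about 16 to 22.
- 65 on MMF: 65 × 0.35 = 22.75 to 65 × 0.50 = 32.5, about 23 to 33.
- Flare, death and drug holds lower these counts. Non-CR patients kept on MMF, as Section 2.4.9 allows, raise them.

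**Still collected after Day 56.** Infections to Day 90 (90 − 56 = 34 of the 42 days), PTLD to Day 270, GVHD staging with diarrhea and nausea/vomiting, liver tests at the later visits, SAEs with no stated end day, and deaths. Among MMF's listed risks, non-serious leukopenia is the one clearly missed; GI symptoms are seen, but not graded as drug toxicity.

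**The case against.** The strongest reply is that the window is a reasonable design choice. Weekly capture lasts as long as the network supplies MMF, later use is followed as usual care, and one fixed window gives every arm equal calendar ascertainment. Section 2.2 names the complications that decide suitability for Phase III (infection, flare, chronic GVHD and early death), and all are collected past Day 56. Toxicity is not a listed secondary endpoint, no between-arm efficacy tests are planned, and Section 5.10 says only that toxicity may matter. Day 98 rests on a suggested taper, and 43% counts taper days as full exposure.

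Much of this stands. It limits the point to a descriptive judgment and supports quoting the 33% and 20% figures beside the 43%. It does not remove the gap: equal calendar windows still cover all planned dosing of three agents and only part of the fourth's, and Section 5.10 does name toxicities. The asymmetry concerns planned dosing only, because Section 2.4.9 also lets non-CR patients in the other arms continue their agent.

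A reader might infer that patients on MMF go unmonitored after Day 56. The documents do not support that: CBCs are labelled standard of care, and the Grade 3–4 hold rule (2.4.1.2) and the ANC rule (2.4.3.5) have no end day. What is lost is recorded data. Nor is safety reporting as a whole cut off, given the data streams that continue.

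**Conclusion.** The gap is real under the protocol's dosing sections: about 42 of 98 days on the suggested taper, 33% when dose-weighted with a linear taper, and S − 28 days in general. What goes missing is chiefly non-serious leukopenia and other expected, non-serious graded toxicity in MMF complete responders. The 16 to 22 patients are an estimate, not a maximum, because the arm may reach 65 and non-CR patients may stay on MMF.

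The Day 28 CR endpoint, the mortality stopping rule and the posterior-probability rules are unaffected. The documents give no late MMF toxicity rate, so the size of any understatement cannot be computed; a reader should not infer that MMF's profile is shown to be biased, only that it could be. This is a cheap improvement of low to moderate priority.

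**What to change.** In Section 4.2.2 and Table 4.2.2:

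- Add a look-back toxicity evaluation (worst grade since the previous visit) at the existing Day 90 and Day 120 visits in all arms, so that windows match. Day 90 alone is not enough: with the ±14-day window it may fall on Day 76, leaving 98 − 76 = 22 nominal MMF days. The earliest Day 120 visit, Day 106, falls after Day 98.
- For patients still on assigned MMF after Day 56, state that standard-of-care CBCs with differential continue until MMF stops, and record the lowest ANC since the previous visit at those two visits. No CBC is added in the other arms.
- Report toxicity by arm separately for the period to Day 56 (weekly capture) and for Days 57–120 (look-back capture).

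Cost: at most 180 × 2 = 360 short toxicity entries, with no new visits. Lowest-ANC entries number about 32 to 45 for the estimated responders (15.75 × 2 to 22.5 × 2), and at most 65 × 2 = 130 if a full arm of 65 were still on MMF. Weekly CBCs over Days 57–98 (assumed interval, six per patient) would be about 95 to 135, as usual care. Most toxicity entries will describe patients off planned study drug. Look-back data are coarser than weekly capture, and late events are harder to attribute when steroids, calcineurin inhibitors or salvage therapy are given at the same time.
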